### **Sample size and justification**

We propose to compare proteomic signatures in 140 knee pain cases. To achieve a Bonferroni  $p < 1.25 \times 10^{-5}$  (adjusting for 4000 tests, i.e. the number of proteins in the Somalogic platform) effect sizes of beta = 0.64 in units of standard deviations are needed to achieve 80% statistical power. Based on the effects seen on radiographic progression (standardized beta = 0.62) these effects appear reasonable and achievable with the proposed sample size.

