## **STATISTICS**

### **Methods**

The chief investigator, co-investigators and the study statistician will evaluate the findings and analysis will be carried out by the co-investigator. The data will be entered into MS Access and analysed using with STATA, SPSS (Statistical Packages for Social Scientists, version 19) and R software. Data will allow exploration of potential relationships between objective sensory measures and molecular findings and/or pain. Several factors that putatively mediate the primary or secondary outcomes are inter-correlated so investigation of their interaction must be ascertained. Simple univariate unadjusted correlations (Pearson/Spearman) and linear regression modelling will be used to examine associations between pain and molecular findings in the synovial fluids at baseline. Multiple linear

regression (MLR) modelling (backward stepwise regression) will be conducted to assess the impact of the significant independent variables and their interactions with the dependent variable.

The results of the study will be available to the study management group. All data will be stored in Academic Rheumatology and will be backed up on the University of Nottingham servers.

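### The Methods section gives no rule for declaring a protein significant; a pre-specified max-T permutation rule would keep the 5% family-wise target and adapt to protein correlation and skew that the planning Bonferroni level ignores

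*Combined protocol and SAP*

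**What the plan says.** All references are to the combined protocol and SAP.

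- Sample size and justification (repeated in the Synopsis): "We propose to compare proteomic signatures in 140 knee pain cases". The significance level is Bonferroni p < 1.25e-5, "adjusting for 4000 tests, i.e. the number of proteins in the Somalogic platform". At that level "effect sizes of beta = 0.64 in units of standard deviations are needed to achieve 80% statistical power", and this is called achievable by reference to an effect on radiographic progression ("standardized beta = 0.62").
- Statistics, Methods: "Simple univariate unadjusted correlations (Pearson/Spearman) and linear regression modelling will be used to examine associations between pain and molecular findings" in the synovial fluid. Backward stepwise multiple regression on the significant variables and their interactions follows. The section names no Bonferroni, false-discovery, permutation or effective-number-of-tests procedure, and does not choose between Pearson and Spearman.
- Same section: "Several factors that putatively mediate the primary or secondary outcomes are inter-correlated so investigation of their interaction must be ascertained". This acknowledges correlation in general. No correlation among proteins is given anywhere, and no transformation of concentrations is named.
- Study Background: pain is recorded on a numerical rating scale at one time point. The Primary endpoint section says only that pain is patient reported.

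**The concern.** The first issue is a gap. The stepwise model takes in the variables found significant, but the analysis text does not say at what level, or by which test, a protein counts as significant. The only available figure is a planning input in another section.

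The second is that, if this figure becomes the analysis rule, it may not be the best way to spend 5%. Proteins measured in one joint fluid are likely to be correlated. A Bonferroni cut-off is then stricter than it needs to be, and true pain proteins near the threshold are missed. Also, a parametric p-value near 1e-5 lies far in the tail, where a bounded, discrete pain score and skewed concentrations can make it inaccurate in either direction. Identifying synovial protein signatures is the primary objective and the sample is fixed at 140, so a rule that uses the observed data structure is worth stating in advance.

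**Working it through.** **Inputs from the documents:** 4000 tests, 140 participants, per-test level 1.25e-5. **Assumed, because the documents do not give them:** two-sided tests, complete data, and all protein correlation structures and distributions below.

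**1. The plan's level.** 0.05/4000 = 1.25e-5, reproduced exactly. The Sidak level for independent tests is 1 − 0.95^(1/4000) = 1.28e-5, so under independence Bonferroni loses almost nothing.

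**2. The cut-off as a correlation.** The two-sided t value at 1.25e-5 on 138 degrees of freedom is 4.533. Critical r = t/√(t² + 138) = 4.533/√158.55 = 0.360.

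**3. Power with normal data.** By Fisher z, power = Φ{[atanh(r) − atanh(c)]·√137}, where c is the cut-off. At r = 0.42, roughly the correlation with 80% power under Bonferroni, and c = 0.360, this is Φ{(0.4477 − 0.3769)·11.705} = Φ(0.83) = 79.6%. The max-T cut-off is the 95th percentile of the largest |r| over 4000 proteins, simulated under each assumed structure:

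| Assumed structure | max-T cut-off | Power at r = 0.42 |
|---|---|---|
| Independent | 0.359 | 80.0% |
| 20 factors, 50% shared variance | 0.356 | 81.1% |
| 10 factors, 50% shared variance | 0.354 | 81.8% |
| 20 factors, 85% shared variance | 0.346 | 84.5% |
| 50 blocks, correlation 0.85 | 0.336 | 87.5% |
| 10 factors, 85% shared variance | 0.334 | 88.0% |

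The gain is about 0 to 2 points in the first three rows and about 5 to 8 in the last three. The family-wise error that Bonferroni actually spends is 3.6% to 4.0% in the moderate structures and 1.4% to 2.5% in the strong ones.

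**4. A separate simulation** (10,000 permutations; effect set to 80% power under Bonferroni):

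- Independent: error spent 4.8%, power 80.2%.
- Blocks of 10 to 200 proteins at r = 0.5: error spent 4.0% to 4.7%, power 80.4% to 81.9%.
- The same block sizes at r = 0.8: error spent 1.2% to 3.6%, power 82.5% to 89.3%.
- One common factor at r = 0.2, 0.4, 0.6 and 0.8: error spent 4.2%, 2.5%, 1.3% and 0.2%; power 81.3%, 86.0%, 90.3% and 97.3%. The last is an extreme case.

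**5. Skewed data under Pearson.** With a rounded 0–10 score and log-normal proteins (log-SD 0.5 to 1.5), the actual per-test error was 0.3 to 0.8 times nominal for symmetric pain and 1.5 to 3.5 times nominal for right-skewed pain. Over 4000 tests the latter means 0.05 × 1.5 = 0.075 to 0.05 × 3.5 = 0.175 expected false positives. With a strongly right-skewed score, simulated family-wise error at 1.25e-5 reached 26% to 51%. In a further run with a right-skewed score and log-SD 1, the max-T cut-off was 0.376 to 0.388, stricter than 0.360; with a symmetric score it was 0.348 to 0.360.

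**6. At the plan's own effect size.** Read as a correlation of 0.62, Bonferroni power is already 99.998%. Read as a slope of 0.64 with residual SD 1, r = 0.64/√(1 + 0.64²) = 0.54 and power goes from 99.6% to 99.9% at the most favourable cut-off in the table. Read as a 70/70 group comparison, power at 0.64 is 24%, rising to 24% to 40% for most structures in step 4. None of these readings gives the stated 80%.

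**The case against.** The strongest case against acting is that nothing in the sample size section is wrong on this point. Bonferroni is a union bound, valid under any dependence, and a max-T threshold cannot be known before the data are in, so 1.25e-5 is a proper planning value. That stands, and the planning value should be kept.

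Three stronger readings are tempting and are not supported:

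- *That the plan assumes independent proteins, or that correlation makes Bonferroni invalid.* The documents state no such assumption, and correlation alone makes Bonferroni conservative, not invalid.
- *That max-T is bound to gain power.* The gain is near zero under independence or weak correlation, the larger figures need strong assumed correlation, and under skew max-T can be stricter than 1.25e-5 and remove rejections. There is almost no gain at 0.62 to 0.64 read as a correlation or slope.
- *That the plan commits to Bonferroni in the analysis.* It commits to no rule.

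It is also fair to say that Spearman, already listed, limits the skew problem. But the plan leaves the choice between Pearson and Spearman open, and the synopsis speaks of parametric regression. Finally, the permutation guarantee applies to the univariate tests. Residual permutation with covariates is approximate, and the stepwise model lies outside it.

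**Conclusion.** The point holds as a low-severity improvement. The firm part needs no assumptions: the analysis section lacks a rule for declaring a protein, and the only multiplicity level is a planning input.

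The size of the benefit is conditional. With normal data, Bonferroni spends about 1.4% to 5% of the family-wise error across the factor and block structures in step 3, and less under more extreme structures. At a true r of 0.42 the recoverable power is about 0 to 2 points under weak or moderate correlation and about 5 to 8 under strong correlation. With strongly skewed pain and untransformed concentrations under Pearson, the error can instead be well above 5%, and the benefit is restored error control. The documents do not show which case applies.

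This does not touch a separate and larger problem: beta = 0.64 at 80% power does not follow from 140 in total, either as a regression (power 99.8%, detectable slope 0.456) or as a 70/70 comparison (24%, both by noncentral t). A reader should not take the permutation rule as a repair for that.

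**What to change.** Add to Statistics, Methods:

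- For the univariate pain–protein tests, proteins are declared associated with pain at step-down max-T (Westfall-Young) permutation-adjusted p < 0.05.
- Use at least 10,000 permutations of the pain score across participants, with a fixed seed. The Monte Carlo standard error of an adjusted p near 0.05 is then √(0.05 × 0.95/10,000) = 0.002.
- Choose one statistic in advance, for example Spearman, or Pearson on log concentrations.
- If covariates are included, use a residual-permutation scheme such as Freedman-Lane and say that it is approximate.
- Label the backward stepwise model secondary and outside this error control.

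In Sample size and justification and the Synopsis, keep 1.25e-5 and call it a planning value only.

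The cost is a short paragraph and a few minutes of computing in R, which the plan already names, with no extra participants. The small downside is that the threshold is known only after the data are in, and under skew it may be stricter than 1.25e-5.

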## SYNOPSIS

Title	Molecular pathways involved in knee pain: an observational study
Short title	Molecular pathways involved in knee pain
Chief Investigator	[name] [name]
Objectives	
Observational Study:
 
[1] To test whether there is an association between proteomic concentrations in the synovial fluid and pain hypersensitivity.
 
[2] To identify proteomic signatures in synovial fluid of centrally vs peripherally driven knee pain.
 
[3] To investigate the relationship of pain hypersensitivity and different proteomic profiles with radiologically-established joint structural changes and muscle strength.
 
[4] To explore the correlation between knee inflammation (effusion, synovial hypertrophy or/and synovial hyper vascularity) and biomarkers of insulin resistance, stress, DNA markers, poor metabolism and knee pain.

Study Configuration	Observational cross-sectional study
Setting	University and secondary care
Sample size estimate	
Observational Study: We propose to compare proteomic signatures in 140 knee pain cases. To achieve a Bonferroni <math>p < 1.25 \times 10^{-5}</math> (adjusting for 4000 tests, i.e. the number of proteins in the Somalogic platform) effect sizes of <math>\beta=0.64</math> in units of standard deviations are needed to achieve 80% statistical power. Based on the effects seen on radiographic progression (standardized <math>\beta=0.62</math>) these effects appear reasonable and achievable with the proposed sample size.
 
Reliability Sub-study: Considering that the study will comprise two different sessions (<math>n=2</math>) featuring one measurement within each and with minimally accepted reliability of <math>p_0=0.5</math> and expected reliability of <math>p=0.8</math>, the minimum sample size has been calculated to be 22 participants. High variability is not expected however, to account for such an occurrence, data will be collected from 25 individuals.

Number of participants	Observational Study: 140 Sub-study: 25
Eligibility criteria	
Inclusion criteria:
 
 
• have the ability to give informed consent
 
• be 45 years or over
 

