Statistical methods	Standard parametric regression methods will be used to assess the levels of association between proteomic profiles, pain and inflammatory markers on ultrasound.

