### Compliance

Compliance will be judged by attendance for study-related appointments and during the study visit based on completion of key study procedures. Participants will be replaced only if they refuse to undertake ultrasound-guided synovial fluid extraction and quantitative sensory testing. Individuals will be given a contact number to contact us if they have any query or wish to reschedule an appointment.

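### The stated 80% power at beta = 0.64 SD does not follow from 140 participants and the planned unadjusted regression, which detects about 0.42; the inputs behind 0.64 are not given

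*Combined protocol and SAP*

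**What the plan says.** The calculation appears twice in the combined protocol and SAP: under Sample size and justification, and in the Synopsis row on the sample size estimate. It opens with "We propose to compare proteomic signatures in 140 knee pain cases", sets the per-test threshold at 1.25e-5 to allow for 4000 proteins, and concludes that "effect sizes of beta = 0.64 in units of standard deviations are needed to achieve 80% statistical power". In support it adds: "Based on the effects seen on radiographic progression (standardized beta = 0.62) these effects appear reasonable and achievable".

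The study is a single cross-sectional cohort in which everyone has knee pain (Study Configuration). On the analysis, the Methods section says: "Simple univariate unadjusted correlations (Pearson/Spearman) and linear regression modelling will be used to examine associations between pain and molecular findings". Backward stepwise multiple regression is to follow. The Synopsis puts it more generally: "Standard parametric regression methods will be used to assess the levels of association between proteomic profiles, pain and inflammatory markers on ultrasound".

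The total number, threshold, number of tests and power are therefore stated. The test, its sidedness, the scale of beta, any covariate input, any group split and the number of evaluable samples are not.

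**The concern.** This is the main study's only power statement. If 0.64 does not follow from the stated inputs, a reader cannot tell which analysis the 140 participants were meant to support.

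Two misreadings are possible. For the regression of pain on a protein, the sentence implies that associations between about 0.42 and 0.64 are underpowered, which is untrue. In the other direction, the Synopsis also lists the objective "To identify proteomic signatures in synovial fluid of centrally vs peripherally driven knee pain". If that were tested as a two-group comparison within the 140, a reader might take 0.64 as the difference the study can detect, and it is not.

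**Working it through.** **Inputs.** From Sample size and justification: N = 140, 4000 tests, 80% power, stated detectable beta 0.64, supporting effect 0.62. From Methods: unadjusted correlation or linear regression of pain on one molecular finding. Assumed here: a two-sided test and all 140 samples usable. Both are varied below.

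**Threshold.** 0.05/4000 = 1.25e-5, as stated. The normal quantiles are 4.369 (two-sided) and 0.842 (80% power), which sum to 5.210.

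**Detectable effect at N = 140**

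- Fisher z: r = tanh(5.210/√(140 − 3)) = tanh(0.445) = 0.418.
- Noncentral t with 138 degrees of freedom and noncentrality b√140, where b is the slope per SD of the protein in residual-SD units: 80% power at b = 0.456. As a standardised beta this is 0.456/√(1 + 0.456²) = 0.415.
- One-sided: 0.404 (t) or 0.407 (Fisher z).
- A simulation of 200,000 data sets at r = 0.42 gave power of 0.801.

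The plan's 0.64 is not reproduced on any of these readings.

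**Power at fixed effects, N = 140, two-sided**

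| Effect | Standardised beta | Residual-SD units |
|---|---|---|
| 0.50 | 0.980 (Fisher z) to 0.987 (t) | 0.910 |
| 0.62 | > 0.9999 | 0.997 |
| 0.64 | > 0.9999 | 0.998 |

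**People needed for 0.64.** Fisher z: (5.210/arctanh 0.64)² + 3 = (5.210/0.758)² + 3 = 50.2, so 51. Noncentral t: 49 for a standardised beta and 76 in residual-SD units. (The normal approximation for the latter, (5.210/0.64)² = 66.3, is too low at so extreme a threshold.)

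**What would give 0.64**

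- *Covariate adjustment.* In residual-SD units the variance inflation must be (0.64/0.456)² = 1.97, so covariates must explain 1 − 1/1.97 = 49% of the protein's variance. On a total-SD scale, assuming the full model explains 0.64² = 41% of the variance in pain, the inflation is about 3.3 and the covariates must explain about 70%.
- *Two separate groups.* A two-sample t-test detects 0.638 SD with 138 per group and 0.634 SD with 140 per group. The plan describes no second group of 140.
- *Fewer usable samples.* About 50 (standardised) or 76 (residual-SD units).

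None of these inputs is in the documents.

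**If fewer samples are usable (assumed counts).** The detectable standardised beta is 0.444 to 0.448 at 120 samples and 0.480 to 0.485 at 100. The evaluable number is an open question, because the Compliance section says "Participants will be replaced only if they refuse to undertake ultrasound-guided synovial fluid extraction and quantitative sensory testing". An attempted aspiration that yields no usable fluid is not replaced under that rule.

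**If two groups were compared within the 140 (assumed 70/70; the plan does not specify this).** The detectable difference is 0.912 SD, power at 0.64 is 24%, and 0.64 would need 2 × 138 = 276 people in total.

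**The case against.** The sample size section names no test. It speaks of comparing signatures, and the Methods section goes on to multiple regression. On that view, setting 0.64 against the simplest listed analysis shows only that the inputs are missing. The intended calculation might be correct, and the error cannot be called conservative while the target analysis is unknown. Keeping 140 would likewise be safe only for the regression of pain on a protein. The restated sentence also chooses pain as the outcome, although the Synopsis objective is pain hypersensitivity and the body's primary objective is to identify signatures. Finally, if the error is conservative and the remedy is wording, it may seem minor.

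Part of this stands. The conservative direction and the adequacy of 140 apply only to the unadjusted regression with most samples usable. The 98 to 99% power at 0.50 holds on the standardised scale; in residual-SD units it is 91%. Retrieving the original inputs is a legitimate alternative to restating the figure.

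The rest does not rescue the sentence. A single cohort of 140 and an unadjusted regression are what the plan describes, and they do not give 0.64. Every route to 0.64 needs an input the plan omits. Because the direction of the error depends on the analysis meant, the plan has to name it.

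**Conclusion.** The concern holds. With 140 analysable samples, a two-sided threshold of 1.25e-5 and the unadjusted regression described, the effect detectable with 80% power is a standardised beta of 0.415 to 0.418 (0.456 in residual-SD units), against the stated 0.64. Power at 0.64 is at least 99.8%, not 80%.

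For that analysis the study is better powered than it claims. The result rests on one protein per model, no covariates and all 140 samples usable. The two-group figures are a conditional caution only.

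A minor related point: on the plan's own figures, the supporting effect of 0.62 falls just short of the 0.64 said to be needed. It would clear a restated 0.42.

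This should be fixed, but it does not threaten the study.

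**What to change.** Leave the sample size at 140 on account of this point. In both the Synopsis and Sample size and justification, do one of the following:

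1. State the test, sidedness, scale of beta, covariate inputs and evaluable number that produce 0.64.
2. Replace the sentence with: *With 140 analysable synovial fluid samples and two-sided p < 1.25e-5 (0.05/4000), the unadjusted linear regression of the pain score on each protein has 80% power for a standardised beta of about 0.42.*

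Re-check the supporting sentence about 0.62 against whichever figure is kept. Do not apply that figure to a contrast of centrally and peripherally driven pain. If such a contrast is intended, it needs its own statement of power.

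The cost is wording in two places, plus retrieving the original power inputs if option 1 is chosen. Recruitment and analysis are unchanged. The limitation of option 2 is that it covers only the unadjusted analysis with all samples usable, so it must be updated if fewer are (about 0.44 to 0.45 at 120, about 0.48 to 0.49 at 100).

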### Primary endpoint

The primary outcome measure is pain measured by patient reported scores.

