## **USER AND PUBLIC INVOLVEMENT**

On 17/05/2017 6 representatives from the Patient and Public Involvement (PPI) MSK group were asked about their views on this project. They all agreed on the need to identify molecular markers to distinguish patient subgroups, not only if this can be conducive to drug development, but more generally they were very appreciative of a stratified medicine approach, and to them it was mostly an issue related to the discrepancies between pain and joint damage seen in their own X-rays. All group members (6/6) indicated their willingness to participate in studies that are conducive to understanding molecular subtypes of OA. Almost all (5/6) would be happy to have synovial aspirations for such a scientific project and would prefer US guided aspiration. They also expressed the view that having diagnostics that can better direct treatment based on molecular test from synovial aspirations or blood should be part of standard practice within the NHS.

The latest versions of the participant facing documentation (PIS, consent form, invitation letter and flyer) has all been forwarded to three PPI representatives who have reviewed and commented on them

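### The sample size is justified by an effect on radiographic progression, an outcome the study does not measure and an effect slightly below the plan's own threshold; no protein-pain effect is given

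*Combined protocol and SAP*

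**What the plan says.** The section Sample size and justification, and the matching entry in the Synopsis, take 140 knee pain cases and a significance level of 1.25e-5 ("adjusting for 4000 tests, i.e. the number of proteins in the Somalogic platform"). They state that "effect sizes of beta = 0.64 in units of standard deviations are needed to achieve 80% statistical power". The only argument that effects of this size are plausible is the next sentence: "Based on the effects seen on radiographic progression (standardized beta = 0.62) these effects appear reasonable and achievable with the proposed sample size". No source is cited for 0.62, and nothing is said about why it should carry over to this study.

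Under Primary endpoint the protocol says: "The primary outcome measure is pain measured by patient reported scores". The Methods section plans Pearson or Spearman correlations, and says that "linear regression modelling will be used to examine associations between pain and molecular findings in the synovial fluids at baseline". The study is cross-sectional (Study Configuration). X-ray morphology is listed under Secondary endpoint; radiographic progression is not. Endpoints are taken at one time-point, with a 120-day follow-up only for participants who go on to surgery.

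**The concern.** There are two problems with the benchmark, of unequal weight.

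The smaller is numerical. The plan sets 0.64 as the effect needed for 80% power and then supports it with an observed 0.62, which does not reach that threshold.

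The larger is that the benchmark belongs to a different outcome. An effect on structural change over time says nothing direct about how strongly a synovial protein is associated with reported pain at one visit. No expected protein-pain effect appears anywhere in the document, so the power statement has no effect estimate behind it for the primary outcome.

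What is at stake is how the results are read. The paragraph tells readers that effects of the needed size are realistic. If protein-pain associations are moderate, most would miss a threshold of 1.25e-5, and a reader relying on this paragraph could take a non-significant protein as evidence of no association.

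**Working it through.** **Inputs.** From Sample size and justification: N = 140, 4000 tests, 80% power, stated effect 0.64, benchmark 0.62. From Methods: correlation and linear regression of pain on synovial findings. Not stated, and assumed here: two-sided tests, all 140 participants analysable.

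**Significance level.** 0.05/4000 = 1.25e-5, as stated. Two-sided z = 4.369; z for 80% power = 0.842; sum = 5.210.

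**Step 1: can 0.64 be reproduced at N = 140?**

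| Reading of beta | Formula | Effect for 80% power |
|---|---|---|
| Correlation (Fisher z) | tanh(5.210/√137) | 0.418 |
| Slope per SD, residual SD 1 | 5.210/√140 | 0.440 |
| Two groups, 70:70 | 5.210 × √(2/70) | 0.881 |

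One-sided tests give 0.407, 0.427 and 0.855. Unequal splits from 40:60 to 20:80 give 0.90 to 1.10. None of the readings tried gives 0.64, and the scale of beta is not defined.

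**Step 2: the benchmark on the plan's own statement.** Suppose that 0.64 does give 80% power, on whatever scale was meant.
- Implied standard error = 0.64/5.210 = 0.1228.
- Power at 0.62 = Φ(0.62/0.1228 − 4.369) = Φ(0.679) = 75%. On the Fisher z scale it is 73%.
- N needed to restore 80% = 140 × (0.64/0.62)² = 149.2, so about 150 (153 on the Fisher z scale).

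**Step 3: power for the planned analysis, from N and alpha alone.** For a one-protein correlation, power = Φ(atanh(r) × √137 − 4.369).

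| r | Power |
|---|---|
| 0.20 | 2% |
| 0.30 | 23% |
| 0.35 | 46% |
| 0.40 | 72% |
| 0.42 (0.418) | 80% |
| 0.62 | over 99.9% |

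Read as a slope per SD with residual SD 1, 0.62 has 99.8% power.

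**Step 4: if a two-group comparison was meant.** Objective 2 in the Synopsis contrasts centrally and peripherally driven pain. With a 70:70 split the standard error is √(2/70) = 0.169.
- At 0.64: Φ(0.64/0.169 − 4.369) = 28%.
- At 0.62: Φ(0.62/0.169 − 4.369) = 24%.
- 80% power needs about 0.88.

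**Scales.** The 75% in Step 2 and the table in Step 3 must not be combined. The first is conditional on the plan's unreproduced 0.64; the second does not use 0.64 at all. If beta is a correlation, Step 3 applies and the 75% does not describe the study's power.

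**The case against.** The strongest reply is that the gap between 0.62 and 0.64 is trivial and that the plan never claims 80% power at 0.62, only that effects of about this size are reasonable. That largely stands: the difference is 5 to 7 points of power and would not justify a change alone.

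A second reply is that structure is not foreign to this study. The primary objective is to identify proteomic signatures, association with pain is the first secondary objective, and structural change is the third. The sample size paragraph speaks of comparing signatures ("We propose to compare proteomic signatures in 140 knee pain cases") and does not name pain. This also stands in part. But the structural objective concerns changes seen on X-ray in a cross-sectional design, while the benchmark is progression. The declared primary outcome is pain, and the Methods section models pain.

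A reader might infer that the study is underpowered, or that its true power is 75%. The documents support neither. The 75% follows only if 0.64 is accepted, and a correlation of 0.62, if it held for pain, would be amply powered at 140.

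A reader might also take the remark under User and Public Involvement about "discrepancies between pain and joint damage seen in their own X-rays" as the protocol conceding that structural effects do not transfer to pain. It reports the views of six lay representatives. It is not the protocol's scientific position and says nothing about protein effects.

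Finally, no section says that a null result would be read as absence of association. That risk is an inference from the paragraph's wording, not a planned interpretation.

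**Conclusion.** The justification does not support the power claim for the primary outcome. The main defect is the outcome mismatch: the cited effect is on radiographic progression, the study does not measure it, and no protein-pain effect is offered in its place. The shortfall of 0.62 against 0.64 is secondary, about 75% against 80% on the plan's own terms.

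This is a defect of justification, not a demonstration that 140 is too few. For the planned one-protein analysis the study has 80% power at about r = 0.42 and little power at r = 0.30 or below. That rests on two-sided testing at 1.25e-5, the Fisher z approximation and no loss of participants to failed aspiration or missing data, for which the plan makes no allowance. Under a two-group reading the position is much weaker, and the document does not say which reading was intended. The point should be corrected, and the correction is inexpensive.

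**What to change.** In both the Synopsis and Sample size and justification, make these changes together:

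1. Delete the sentence that relies on radiographic progression.
2. Replace the 0.64 statement with the detectable effect for the planned analysis on a defined scale: r of about 0.42 for 80% power, two-sided at 1.25e-5, with 140 analysable participants.
3. Add the power at r = 0.20, 0.30, 0.35 and 0.40 (2%, 23%, 46% and 72%).
4. State that moderate protein-pain associations would usually be missed, so a non-significant protein is not evidence of no association.
5. If a two-group comparison was meant, say so and restate the power for it: for a 70:70 split, about 28% at 0.64, 24% at 0.62, and 80% at about 0.88.

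Changes 1 and 2 must not be separated. Leaving 0.64 in place beside a table that reaches 80% near 0.42 would make the paragraph contradict itself.

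The cost is wording only. The justification loses its external benchmark; the sample size and procedures do not change.
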